## Document History

Document	Version	Summary of Changes
Original protocol	1.0	Not applicable (N/A)
Amendment 1		
Amendment 2		

Amendments incorporate all revisions to date, including amendments made at the request of country health authorities, institutional review boards/ethics committees (IRBs/ECs), etc.

# 1 PROTOCOL SUMMARY

## 1.1 Synopsis

### Short Title:

A bioequivalence study of 21 mg nicotine transdermal patches (NicoDerm CQ, GSK Dungarvan) compared to the current marketed 21 mg nicotine transdermal patches (NicoDerm CQ, Alza) in healthy adult smokers.

### Background and Rationale:

NicoDerm CQ patch is manufactured by Alza. GSK will submit an application to support the change of manufacturing site from Alza to Dungarvan.

The purpose of this study is to assess the bioequivalence of the 21mg nicotine transdermal patch from GSK Dungarvan (Test) compared to the 21mg nicotine transdermal patch currently manufactured by Alza (Reference).

### Objectives and Endpoints:

Objectives	Endpoints
Primary	
Demonstrate the bioequivalence of the 21-mg nicotine transdermal patch from GSK Dungarvan (Test) compared to the 21 mg nicotine transdermal patch manufactured by Alza (Reference)	
 
• <math>C_{max}</math> (The maximum observed post-dose concentration; obtained without interpolation)
 
• <math>AUC_{0-t}</math> (The area under the plasma concentration versus time curve calculated from time 0 to the last measurable sampling time point, t,)
 
• <math>AUC_{0-inf}</math> (The area under the plasma concentration versus time curve calculated from time 0 to infinity)
 

Secondary	
Pharmacokinetics	
Assess the pharmacokinetic profile of the patches	
 
• <math>\lambda_z</math> (The terminal elimination rate constant)
 
• <math>t_{max}</math> (The time of the maximum observed post-dose concentration)
 
• <math>t_{1/2}</math> (The elimination half-life computed as <math>t_{1/2} = \ln(2) / \lambda_z</math>)
 

Adhesion	
To monitor adhesion of the patches to the skin	Adhesion score
Safety	

Assess the safety profile (local and systemic) of both products	
 
• Monitoring and recording of adverse events
 
• Physical examination
 
• Vital signs
 
• Laboratory tests
 

---	---

**Study Design:**

This is a 2-arm, single center, single dose, open-label, randomized, two-sequence, two-period crossover, bioequivalence study in healthy adult smokers that have smoked more than 10 cigarettes per day for 1 year prior to inclusion.

Subjects will be randomly assigned to receive a single-dose of one of the following treatments which will follow a cross-over design:

Treatment A: 21 mg/24h NicoDerm CQ (GSK Dungarvan)-Test

Treatment B: 21 mg/24h NicoDerm CQ (Alza)- Reference

In each treatment period, each subject will be dosed once, i.e., a single NicoDerm patch will be placed under fasted conditions to the upper part of the back for a total duration of 24 hours, and then removed. Blood will be sampled regularly at scheduled times for 36 hours following patch application. The pharmacokinetic profile may be altered when a patch loses its adherence to the skin. Therefore, the adhesion of the patch should be monitored. Adhesion will be assessed five times: within 5 minutes from patch application and approximately 6, 12 and 18 hours after patch application and immediately prior to patch removal.

Carry-over effects will be avoided by a wash-out interval of at least 2 days (but no more than 4 days) from patch removal in the first treatment period to subsequent patch application.

The study will consist of an ambulant screening day within 21 days prior first patch application. Subjects will be confined in the study facility from 48 hours pre dosing until 36 hours post last dosing; pharmacokinetic (PK) blood samples will be obtained at predose (within 1 hour before dosing), 30 minutes and 1, 2, 3, 4, 5, 6, 8, 10, 12, 14, 16, 18, 20, 24, 25, 26, 27, 28, 30, 32, and 36 hours after administration of the patch.

For each subject the duration of study participation is 27 days of which up to 8 days confined.

Subjects are to abstain from smoking during the confinement period and be subject to random measurements of expired carbon monoxide (CO) to confirm abstinence. The CO levels must be  $\leq 10$  ppm throughout the study.

**Study Products:**

	Test Product	Reference Product
Product Name	NicoDermCQ	

	21 mg /system of 22 cm  surface area	NicoDermCQ (USA commercial product) 21 mg /system of 22 cm  surface area
Dose/Application	One application	One application
Route of Administration	Topical	Topical

**Type and Planned Number of Subjects:**

A sufficient number of subjects will be screened to randomize approximately 20 to ensure a minimum of 12 evaluable subjects complete the entire study.

**Statistical Methods:**

The PK analysis set will be used for the PK evaluations. It includes all randomized subjects of the PK population, for which the relevant predose-adjusted PK parameters (at least one AUC or Cmax) can be derived.

The PK parameters that will be used in the primary analyses are AUC0-t, AUC0-inf and Cmax.

The null and alternative hypotheses to be tested in the primary analyses are:

H0: The (geometric) mean AUC0-t (likewise AUC0-inf and Cmax) of (Test) is less than 80% or greater than 125% of that of (Reference).

H1: The (geometric) mean AUC0-t (likewise AUC0-inf and Cmax) of (Test) is between 80% and 125% of that of (Reference).

A linear mixed effects model will be fit to the log-transformed PK variables (AUC0-t, AUC0-inf and Cmax), as the dependent variable, and treatment, and period as fixed effects. Subject nested within sequence will be a random effect. Least squares estimates of treatment effects will be calculated and a 90% confidence interval (CI) for the treatment difference will be computed. The treatment difference and its CI will be exponentiated to obtain the ratio of the geometric means between the test and reference products and its CI.

Bioequivalence between the test and reference treatments will be concluded if the 90% confidence interval for the ratio of the means for each of the PK parameters AUC0-t, AUC0-inf, and Cmax of the nicotine profiles lie entirely within the interval 0.8 to 1.25.

**1.2 Schedule of Activities**

The schedule of activities table provides an overview of the subject visits and study procedures.

The investigator may conduct unplanned visits and procedures in addition to those listed on the schedule of activities, to conduct evaluations or assessments required to protect the well-being of the subject and maintain study integrity.

**Table 1-1 Schedule of Activities**

Procedure/Assessment	Screening	Period 1				Wash Out	Period 2				End of study visit*
		Visit	1	2	3		3	4	5	6	
Study Day	-21 to -2	-2	-1	1	2	3	4	5	6	6	
Confinement c		x	x	x	x	x	x	x	x		
Informed consent	x										
Demography	x										
Medical History i	x		x								
Physical Exam a	x		x					x		x	
Height and Weight	x										
Vital signs b	x	x	x	x	x	x	x	x	x	x	
12-lead ECG	x										
Laboratory tests	x									x	
COVID-19 test h	x	x								x	
Virology	x										
Pregnancy test l	x	x					x			x	
Urine illicit drug screen	x	x									
Alcohol breath test	x	x									
Inclusion/Exclusion Assessment	x	x									
Continued eligibility							x e				
Randomization				x							
Patch application				x				x			
Patch removal					x				x		
PK blood sampling c				x	x			x	x		
Patch adhesion assessment d				x	x			x	x		
Expired CO g		x	x	x	x	x	x	x	x		
Concomitant treatments	x	x	x	x	x	x	x	x	x	x	
Adverse events f	x	x	x	x	x	x	x	x	x	x	
Study conclusion										x	

Abbreviations: ECG, CO, PK

**Footnotes:**

\* These assessments are also to be conducted for subjects who discontinue study drug. End of Study visit will occur before discharge, on study Day 6

a Including site application examination; full physical examination at screening and final visit and examination of the areas on the back only before each patch application

b Including body temperature; body temperature will be measured every day; all vital signs will be assessed at screening, pre-treatment in each treatment period (1 – 30 minutes before drug administration) and final visit.

c PK blood samples will be collected at predose (within 1 hour before dosing) and at 30 minutes and at 1, 2, 3, 4, 5, 6, 8, 10, 12, 14, 16, 18, 20, 24, 25, 26, 27, 28, 30, 32, and 36 hours after administration of the patch. See [section 8.2](#)

d Within 5 minutes from patch application and approximately 6, 12, 18 hours post application and before patch removal (24 hours after patch application)

e At the discretion of the Investigator, the subjects could continue the study if any deviation to the inclusion/exclusion criteria does not anticipate to alter study integrity.

f Adverse Events (AEs) and therefore all Serious Adverse Events (SAEs) will be collected immediately after a subject provides consent to participate in the study by the completion of the Informed Consent Form (ICF).

g Breath CO measurement taken upon check-in, on day -2 and immediately prior to randomization in Period 1, immediately prior to dosing in Period 2, one during the wash-out, 3 times randomly in each period and immediately after the last PK sample in each period.

h Before dosing two consecutive approved (Locally approved tests (PCR or Antigen) will be performed: one test at screening and one test at check-in (Day-2). If the second test is > 72 hours prior to unit admission, subjects should be advised to self-quarantine until entrance to the unit while awaiting final testing clearance. Subjects who report symptoms suggestive of COVID-19 while in the research unit should be isolated in the unit or at home and tested for COVID-19 infection using an approved molecular test. One test (Locally approved tests (PCR or Antigen) should be performed before releasing the subject from the unit i.e. at early discontinuation or end of study.

i Includes Smoking history

l Serum pregnancy test at screening and end of study and CLIA-waived urine pregnancy test at check-in Day -2 and Day 4

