## 3 STUDY OBJECTIVES AND ENDPOINTS

**Table 3-1 Study Objectives and Endpoints**

Objectives	Endpoints
Primary	
Demonstrate the bioequivalence of the 21 mg nicotine transdermal patch from GSK Dungarvan (Test) compared to the 21 mg nicotine transdermal patch manufactured by Alza (Reference)	
 
<math>C_{max}</math> (The maximum observed post-dose concentration; obtained without interpolation)
 
<math>AUC_{0-t}</math> (The area under the plasma concentration versus time curve calculated from time 0 to the last measurable sampling time point, t, computed using the linear trapezoidal rule)
 

	
 
AUC0-inf (The area under the plasma concentration versus time curve calculated from time 0 to infinity)
 

Secondary	
Pharmacokinetics	
Assess the pharmacokinetic profile of the patches	
 
<math>\lambda_z</math> (The terminal elimination rate constant)
 
<math>t_{max}</math> (The time of the maximum observed post-dose concentration)
 
<math>t_{1/2}</math> (The elimination half-life computed as <math>t_{1/2} = \ln(2) / \lambda_z</math>)
 

Adhesion	
To monitor adhesion of the patches to the skin	Adhesion score
Safety	
Assess the safety profile (local and systemic) of both products	
 
Monitoring and recording of adverse events
 
Physical examination
 
Vital signs
 
Laboratory tests
 

This study will be considered successful if bioequivalence between the Test and Reference treatments conclude that the 90% confidence intervals for the ratio of the means of the primary pharmacokinetic parameters AUC0-t and AUC0-inf and Cmax of the nicotine profiles lie completely within the range 0.8-1.25.

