## 6.2 Administration

Only subjects enrolled in the study may receive study products and only authorized site staff may supply or administer study products. All study interventions must be stored in a secure, environmentally controlled, and monitored (manual or automated) area in accordance with the labeled storage conditions with access limited to the authorized site staff only.

The patches will be applied according to the instruction provided in the US prescribing information (OTC Drug Facts label & Package Insert).

NicoDerm CQ patch (either Test or Reference patch according to randomization list) will be applied after an overnight fasting period of at least 10 hours, with subjects in a sitting position.

Patches will be applied on morning of study Day 1 of each treatment period. The patch will be applied to a clean and dry skin site on the upper back. The site must be relatively free of hair and free of any tattoos, scarring, or redness and free any conditions which in the opinion of the investigator may impact patch adhesion. Hair at the intended patch site could be clipped but cannot be shaved. To ensure adequate adhesion of the patch, the patch should be pressed down firmly on the skin for at least 10 seconds, making sure all the edges are attached. Staff will wash their hands after application. After application, patches may not be touched. No patch reinforcement or over taping is allowed.

Patches will be removed 24 hours after each application. Staff will wash their hands after patch removal.

The patch that will be applied during Period 2 will not to be applied to the same position as the patch that was applied during Period 1 but on the upper back of the contralateral side of the body.

To standardize the conditions on pharmacokinetic sampling days, all subjects will be required to refrain from lying down (except when required for blood pressure, pulse rate measurements), eating, and drinking beverages excepting water which is allowed from 1 hour post dosing, for the first 4 hours after dosing.

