- Spontaneous reporting of adverse events and those elicited by asking subjects to respond to a non-leading question such as “How do you feel?” will be assessed and any AEs recorded in the CRF.

### 8.2.4 Visit 2/Day 2

- Collect blood samples for pharmacokinetic analysis at 24, 25, 26, 27, 28, 30, 32, and 36 hours post dosing at Day 1 continuing into Day 2. A deviation of  $\pm 3$  minutes will be accepted for the blood samples. Time of blood sampling will be recorded in the CRF
- Conduct adhesion assessment directly before patch removal (24 hours after patch application)
- Patch removal and record in the CRF

- As needed for period 1, collect 3x random CO measurements and one measurement after the last PK sample (see section [9.5 Expired Carbon Monoxide \(CO\) measurement](#)), and record in the CRF
- Obtain oral body temperature. The results for each measurement will be recorded in the CRF.
- Changes in concomitant medication or non-drug treatments/procedures will be documented in the CRF.
- Spontaneous reporting of adverse events and those elicited by asking subjects to respond to a non-leading question such as “How do you feel?” will be assessed and any AEs recorded in the CRF.
- Meals as required. Time and consumption of meals will be recorded on CRF.

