### 8.2.5 Washout period

Washout period of at least 2 days after the first dose.

- Obtain oral body temperature. The results for each measurement will be recorded in the CRF.
- Collect expired CO measurement. Result will be recorded on the CRF.
- Meals as required. Time and consumption of meals will be recorded on CRF.
- Changes in concomitant medication or non-drug treatments/procedures will be documented in the CRF.
- Spontaneous reporting of adverse events and those elicited by asking subjects to respond to a non-leading question such as “How do you feel?” will be assessed and any AEs recorded in the CRF.

### 8.2.6 Visit 3/Day 4

- Obtain oral body temperature. The results for each measurement will be recorded in the CRF.
- Collect expired CO measurement prior to continued eligibility check. Result will be recorded on the CRF.
- Collect urine pregnancy test for all females of childbearing potential. The results will be recorded in the CRF
- Meals as required. Time and consumption of meals will be recorded on CRF.
- Changes in concomitant medication or non-drug treatments/procedures will be documented in the CRF.
- Spontaneous reporting of adverse events and those elicited by asking subjects to respond to a non-leading question such as “How do you feel?” will be assessed and any AEs recorded in the CRF.

### 8.2.7 Visit 3/Day 5

**Prior to dosing**, within 1 hour of patch application, the following procedures will be completed and recorded on the CRF:

- Brief physical examination including evaluation of general appearance, heart, lung. The results will be recorded in the CRF.
- Review Inclusion and Exclusion criteria and record in the CRF
- Collect expired CO measurements. Result will be recorded on the CRF.
- Collect supine blood pressure and pulse rate.
- Collect respiratory rate, oral body temperature and record in the CRF.
- Collect a blood sample for pharmacokinetic analysis. Time of blood sampling will be recorded in the CRF.
- After all pre-dose procedures have been completed, administer the investigational product (see [Study Treatments and Administration Sections](#)) and record in the CRF.

**After dosing**, the following procedures will be completed and recorded in the CRF:

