#### **Adverse events:**

The assessment of safety will be based on the frequency and severity of AEs that are emergent after subject randomization, including all application site reactions.

The incidence of treatment-emergent AEs will be tabulated after grouping by preferred term within System Organ Class (SOC). AEs will be summarized as the number and percentage of subjects having any AE, an AE by SOC, and an AE by preferred term within SOC. The subset of AEs suspected of a relationship to study patch application will be summarized similarly. All treatment emergent AEs will also be tabulated by severity. Each AE will be attributed to the patch whose application immediately preceded onset of the AE.

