### 10.5 Physical Examination

A full physical examination will be performed at screening and Day 6 at the End of Study visit. A brief physical examination will be performed on Day -1 and Day 5 and will be focused on general appearance, the respiratory and cardiovascular systems, as well as towards subject reported symptoms.

A full physical examination will include head, ears, eyes, nose, mouth, skin, heart and lung examinations, lymph nodes, gastrointestinal, musculoskeletal, vascular and neurological systems. A brief physical examination will be focused on general appearance, heart (Cardiovascular), and lung (Respiratory) findings.

Any untoward findings identified on physical exams conducted after the administration of the first patch application will be captured as an adverse event, if those findings meet the definition of an adverse event.

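### No application-site inspection is scheduled at patch removal, and the documents disagree on whether the pre-application examinations cover the skin site, so local reactions are formally looked for much later in Period 1 than in Period 2

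*Protocol*

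**What the plan says.** The safety objective in Protocol Table 3-1 is: "Assess the safety profile (local and systemic) of both products". Its endpoints are adverse events, physical examination, vital signs and laboratory tests. Protocol 12.3.3 bases the safety assessment on adverse events, "including all application site reactions". SAP 10.1 repeats this and adds a table by relationship to the application site.

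The Physical Exam row of Table 1-1 is marked at screening, Day -1, Day 5 and the end-of-study visit only. Its footnote a says that the row takes in the application site, with a full examination at the first and last of these visits and "examination of the areas on the back only before each patch application".

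The procedure sections describe the two middle examinations differently. Protocol 8.2.2 (Day -1) and 8.2.7 (Day 5) both call for: "Brief physical examination including evaluation of general appearance, heart, lung". SAP 10.5 says "A brief physical examination will be performed on Day -1 and Day 5 and will be focused on" general appearance, the respiratory and cardiovascular systems, and symptoms the subject reports. Neither names the skin site. Protocol 8.1.6, by contrast, lists a skin-site evaluation explicitly at screening.

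On wear time, Protocol 6.2 says: "Patches will be removed 24 hours after each application". The removal-day lists (8.2.4 for Day 2, 8.2.8 for Day 6) give an adhesion score directly before removal, then "Patch removal and record in the CRF", and also blood samples, CO, temperature and the AE question. No inspection of the skin is listed. Section 6.2 places the second patch on the opposite side of the upper back.

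**The concern.** A transdermal patch can cause reactions at the skin it covered, and the natural moment to see them is when the patch is lifted. The plan sends a trained evaluator to the patch at that moment to score adhesion, but asks for no record of the skin beneath it.

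What remains is a set of examinations at other times, on whose content the documents disagree. If footnote a governs, the back is examined before the second application. Because the new patch goes on the other side, that look need not include the used site. If 8.2.7 and SAP 10.5 govern, the first formal examination of the Period 1 site may be the full examination at exit, which includes skin (Protocol 9.2.6).

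Two things are at stake. A mild or short-lived reaction that the subject does not mention and no one happens to note can be gone before anyone formally looks. And the chance of seeing it differs between the two applications in the same subject. No field records that the site was inspected and found clear, so an empty AE record cannot separate no reaction from no inspection.

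**Working it through.** **Inputs**
- Wear time 24 h in each period (Protocol 6.2).
- Nominal days: application on Days 1 and 5, removal on Days 2 and 6 (Table 1-1).
- Pre-dose procedures within 1 h before application (8.2.7).
- Washout at least 2 and at most 4 days from first removal to second application (4.1), i.e. 48 to 96 h.
- Exit examination on Day 6 before discharge, hour not fixed (Table 1-1 footnote, 8.3). It is set here at the end of confinement, 36 h after the second application (1.1, 4.1).

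**Nominal timeline**, first application = 0 h
- First removal: 24 h.
- Second application: 4 × 24 = 96 h. Washout = 96 − 24 = 72 h (3 days), inside the stated 2 to 4 days, so the schedule agrees with section 4.1.
- Second removal: 96 + 24 = 120 h.
- Exit: 96 + 36 = 132 h.

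**Delay from removal to next formal examination**
- Period 1, Day 5 examination includes the used site: 95 − 24 = 71 h to 96 − 24 = 72 h.
- Period 1, site first seen at exit: 132 − 24 = 108 h.
- Period 2, at exit: 132 − 120 = 12 h.

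The 108 h and 12 h are upper values, because the exit examination could take place earlier on Day 6.

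**Over the allowed washout W**, the Period 1 delay is W − 1 to W at the pre-dose examination, or up to W + 36 at exit.
- W = 48 h: 47 to 48 h, or 84 h.
- W = 96 h: 95 to 96 h, or 132 h.

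The Period 1 range is therefore about 47 to 96 h on one reading and 84 to 132 h on the other. The Period 2 figure stays at 12 h. Section 8.2.5 counts the 2 days from the first dose rather than from removal. Read alone, it allows W = 24 h, giving 23 to 24 h, or 60 h. Sections 4.1 and 8.2.5 need to be reconciled.

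**Does the delay favour one product?** Mean delay per product, with a subjects taking Test first and b taking Reference first, Period 1 delay d and Period 2 delay 12 h:

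Test = (a·d + 12b)/(a + b); Reference = (12a + b·d)/(a + b).

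- Balanced (10/10 or 6/6), d = 72: (72 + 12)/2 = 42 h for each product.
- Balanced, d = 108: (108 + 12)/2 = 60 h for each product.
- Illustrative 7/5 split of 12 completers, d = 72: (504 + 60)/12 = 47 h against (84 + 360)/12 = 37 h.
- The same split, d = 108: (756 + 60)/12 = 68 h against (84 + 540)/12 = 52 h.

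The 7/5 split is an assumption. The plan allows for a 40% loss from about 20 randomized to 12 evaluable (12/0.60 = 20), so some imbalance is possible. Subjects who stop early receive the end-of-study assessments (Table 1-1 footnote), so the Period 1 delays apply to those who go on to Period 2.

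**The case against.** The strongest reply is that examination is only one route to local safety. AEs are collected on every confined day. Protocol 10.4 requires each subject to be questioned and all directly observed AEs to be reported. Staff remove the patch, and an evaluator is at the site just before. Site reactions are part of the AE analysis, and each AE is attributed to the patch applied most recently before its onset. A visible reaction at removal should therefore reach the AE record. This stands, and it rules out two readings that a reader might be tempted by: that the local-safety objective is not met, and that local reactions rest only on a general question to the subject.

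The delay also follows period and not product. Randomization to two sequences places each patch in both periods, so one cannot infer a systematic bias between Test and Reference. Nor are only the Period 2 data usable, since a Day 5 look at the used site would still show persisting reactions. Physical examination findings are only to be listed (Protocol 12.3.3), so no formal within-subject comparison of skin findings is planned that could be undermined.

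Finally, footnote a opens by including the site in the examination row, the brief examination is described in non-exhaustive terms, and 6.2 requires the new site to be free of redness. Someone will thus look at the new site before application. That weakens the 108 h reading but does not remove it, because none of these passages clearly requires the used site to be examined on Day 5. The objection also leaves untouched the absence of any instruction or field for the skin at removal.

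**Conclusion.** The point holds as a gap in standardization and timing. No application-site inspection is scheduled at removal in either period. Footnote a conflicts with Protocol 8.2.2 and 8.2.7 and SAP 10.5 on the content of the Day -1 and Day 5 examinations. The next formal look at the Period 1 site comes at about 72 h, or up to 108 h, after removal on nominal days, against at most about 12 h in Period 2. Which Period 1 figure applies depends on whether Day 5 covers the used site.

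The consequence is lower sensitivity to mild or transient local reactions, more so in Period 1 (about 20 of the 40 planned applications). With balanced sequences the mean delay is equal for the two products. With unequal completion a modest difference could arise, such as 47 against 37 h or 68 against 52 h in the 7/5 illustration. The documents give no time course or rate for local reactions, so the number that would go unrecorded cannot be estimated. The pharmacokinetic primary analysis is not affected. This should be corrected because a stated objective can be served better at almost no cost, not because the objective fails as planned.

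**What to change.** Add to Protocol 8.2.4 and 8.2.8, and to Table 1-1, an inspection of the application site at patch removal in both periods, done by the staff already present for the adhesion score. Record visible reaction yes or no, with a description if yes, and enter an AE where the definition is met. Add a table of the result by treatment to the SAP. This brings the delay to about 0 h in both periods and gives a recorded negative.

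Reconcile footnote a with Protocol 8.2.2 and 8.2.7 and SAP 10.5, so that it is clear whether the Day 5 examination covers the used site, the new site or both. Reconcile the washout wording in 4.1 and 8.2.5 at the same time.

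The cost is a minor amendment and one CRF field, with no extra visit or staff. The downside is that slightly more mild skin findings will be reported.
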